7.2.1. Selection and Timing of Doses

Investigational product will be provided to patients following randomization at Visit 3 (Week 0).

The tablet(s) should be taken orally each day, without regard to food and if possible, at approximately the same time every day. Special timing considerations of administration of investigational product relative to PK sample collection at study visits are described in Section 9.5.

For patients taking concomitant cholestyramine it is recommended that patients take baricitinib at least 1 hour before or 4 to 6 hours after cholestyramine.

7.3. Blinding

This is a double-blind study. To preserve the blinding of the study, a minimum number of Lilly personnel will see the randomization table and treatment assignments before the study is complete. All study assessments will be performed by study personnel who are blinded to the patient's treatment group. Except in clinical circumstances where unblinding is required, the patients, investigators, Lilly study team, and any personnel interacting directly with patients or investigative sites will remain blinded to baricitinib and placebo assignment. Every effort should be made to preserve the blind unless there is a compelling reason that knowledge of the specific treatment would alter the medical care of the patient.

In case of an emergency, the investigator has the sole responsibility for determining if unblinding of a patient's treatment assignment is warranted for medical management of the event. Patient's safety must always be the first consideration in making such a determination. Where feasible and when the timing of the emergent situation permits, the investigator should attempt to contact the Lilly medical monitor before unblinding a subject's treatment assignment. If a patient's treatment assignment is unblinded, Lilly must be notified immediately. If the investigator decides that unblinding is warranted, it is the responsibility of the investigator to promptly document the decision and rationale and notify Lilly as soon as possible.

Emergency unblinding for AEs may be performed through the IWRS. This option may be used ONLY if the patient's well-being requires knowledge of the patient's treatment assignment. All unblinding events are recorded and reported by the IWRS. If an investigator, site personnel performing assessments, or patient is unblinded, the patient must be discontinued from the study. In cases where there are ethical reasons to have the patient remain in the study, the investigator must obtain specific approval from a Lilly designated medical monitor for the patient to continue in the study.

7.4. Preparation/Handling/Storage/Accountability

All investigational product (used and partially used) will be returned to the sponsor or destroyed at the site level with the sponsor’s written approval. In some cases, sites may destroy the material if, during the investigative site selection, the evaluator has verified and documented that the site has appropriate facilities and written procedures to dispose of clinical trial materials.

Follow storage and handling instructions on the investigational product packaging.

7.5. Treatment Compliance

Patient compliance with study medication will be assessed at Visit 4 through Visit 7 and at Early Termination during the treatment period by counting returned tablets and direct questioning. Deviation(s) from the prescribed dosage regimen should be recorded in the electronic case report form (eCRF).

The patient will be considered significantly noncompliant if he or she misses more than 20% of study medication during the study, unless the patient’s investigational product was withheld by the investigator for safety reasons. Similarly, a patient will be considered significantly noncompliant if he or she is judged by the investigator to have intentionally or repeatedly taken more than the prescribed amount of medication.

7.6. Concomitant Therapy

Patients will maintain their usual medication regimen for PBC and for any other concomitant diseases throughout the study unless specifically excluded in the protocol (Section 6.2, Exclusion Criteria). Patients taking these medications should be on chronic stable doses at the time of randomization, as specified by the Inclusion Criteria (Section 6.1, Inclusion Criteria).

All concomitant medication, whether prescription or over the counter, used at baseline and/or during the course of the study must be recorded on the relevant eCRF. Any changes to the patient’s medication must be discussed with the investigator. Patients should be instructed to consult the investigator or other appropriate study personnel at the site before taking any new medications or supplements during the study.

7.6.1. Permitted Medications and Procedures

[REDACTED]

[REDACTED]

[REDACTED]

[REDACTED]

[REDACTED]

[REDACTED]

7.6.2. Prohibited Medications and Procedures

[Redacted text block containing multiple paragraphs and bulleted lists under section 7.6.2]

7.7. Treatment after the End of the Study

7.7.1. Treatment after Study Completion

Baricitinib will not be made available to patients after conclusion of the study.

8. Discontinuation Criteria

8.1. Discontinuation from Study Treatment

8.1.1. Interruption of Investigational Product

In some circumstances, it may be necessary to temporarily interrupt treatment as a result of AEs or abnormal laboratory values that may have an unclear relationship to investigational product. It is recommended that the investigator consult with Lilly (or its designee) before temporarily interrupting therapy for reasons other than those defined in [Table JAIV.4](#). Unless otherwise specified, retest timing and frequency is at the investigator's discretion.

Investigational product that was temporarily interrupted because of an AE or abnormal laboratory value not specifically covered in [Table JAIV.4](#) may be restarted at the discretion of the investigator. Investigational product must be held in the following situations and may only be resumed as noted in the table.

Table JAIV.4. Criteria for Interruption of Investigational Product

Hold Investigational Product if the Following Abnormalities Occur:	Investigational Product May be Resumed When:
WBC count <2000 cells/ μ L (<2.00 x 10 ³ / μ L or <2.00 GI/L)	WBC count \geq 2500 cells/ μ L (\geq 2.50 x 10 ³ / μ L or \geq 2.50 GI/L)
ANC <1000 cells/ μ L (<1.00 x 10 ³ / μ L or <1.00 GI/L)	ANC \geq 1200 cells/ μ L (\geq 1.2 x 10 ³ / μ L or \geq 1.2 GI/L)
Lymphocyte count <500 cells/ μ L (<0.50 x 10 ³ / μ L or <0.50 GI/L)	Lymphocyte count \geq 750 cells/ μ L (\geq 0.75 x 10 ³ / μ L or \geq 0.75 GI/L)
Platelet count <75,000/ μ L (<75 x 10 ³ / μ L or <75 GI/L)	Platelet count \geq 100,000/ μ L (\geq 100 x 10 ³ / μ L or \geq 100 GI/L)
ALT or AST >3X ULN for patients with normal ALT or AST at baseline	ALT and AST return to \leq 3X ULN and investigational product is not considered the cause of enzyme elevation.
ALT or AST > 3X baseline value for patients with ALT or AST >ULN at baseline	ALT and AST return to \leq 3X baseline value for patients with increased baseline and investigational product is not considered the cause of enzyme elevation.
Hemoglobin <8 g/dL (<80.0 g/L)	Hemoglobin \geq 9 g/dL (\geq 90.0 g/L)
eGFR <50 mL/min/1.73 m ²	eGFR \geq 60 mL/min/1.73 m ²
Symptomatic herpes zoster	All skin lesions have crusted and are resolving
Infection that, in the opinion of the investigator, merits the IP being withheld ^a	Resolution of infection that, in the opinion of the investigator, merits the IP being restarted
Clinical features of VTE (deep vein thrombosis or pulmonary embolism) are present	After diagnosis of VTE has been excluded. If diagnosis of VTE is confirmed, study treatment must be permanently discontinued

Abbreviations: ALT = alanine aminotransferase; ANC = absolute neutrophil count; AST = aspartate aminotransferase; eGFR = estimated glomerular filtration rate; IP = investigational product; ULN = upper limit of normal; VTE = venous thromboembolism; WBC = white blood cell.

^a Permanent discontinuation of IP should be considered for patients who develop a serious infection that, in the opinion of the investigator, would pose an unacceptable risk if IP were resumed.

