8.1.2. Permanent Discontinuation from Study Treatment

Possible reasons leading to permanent discontinuation of investigational product:

- **Subject Decision**
 - the patient requests to discontinue investigational product.
- **Investigator Decision**
 - the investigator decides that the patient should be discontinued from investigational product
- **Discontinuation due to a hepatic event or liver test abnormality:** Patients who are discontinued from investigational product because of a hepatic event or liver test abnormality should have additional hepatic safety data collected via eCRF. Details on continued hepatic monitoring are provided in Section 9.4.7.

If multiple values are obtained during screening, the highest value prior to receipt of investigational product will be used as baseline. Discontinuation of the investigational product for abnormal liver tests **should be** considered by the investigator when a patient meets one of the following conditions after consultation with the Lilly designated medical monitor:

- a. For patients with **baseline normal ALT and/or AST**, the following will result in discontinuation:

single laboratory test	ALT or AST >8 x ULN
single laboratory test	ALT or AST >3 x ULN and TBL >2 x ULN or International Normalized Ratio (INR) >1.5
single laboratory test	ALT or AST >3 x ULN with the appearance of fatigue, nausea, vomiting, right upper-quadrant pain or tenderness, fever, rash, and/or eosinophilia (>5%)
confirmed laboratory test (2 tests)	ALT or AST >2 x ULN and no other known cause.
during temporary interruption of IP	ALT or AST >5 x ULN for more than 2 weeks after temporary interruption of investigational product

- b. For patients with **baseline elevated ALT and/or AST**, the following will result in discontinuation:

confirmed laboratory test (2 tests)	ALT >5 x baseline, or >400 U/L (whichever occurs first)
confirmed laboratory test (2 tests)	ALT >3 x baseline and TBL >2 x ULN or INR >1.5
confirmed laboratory test (2 tests)	ALT >3 x baseline with appearance of severe fatigue, nausea, vomiting, right upper-quadrant abdominal pain, fever, rash, and/or eosinophilia (>5%)
confirmed laboratory test (2 tests)	ALT or AST >2 x ULN and no other known cause
confirmed laboratory test (2 tests)	TBL >1.5 x baseline upon retesting and no other known cause
during temporary interruption of IP	ALT >4 x baseline or >300 U/L (whichever occurs first) for more than 2 weeks after temporary interruption of investigational product

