9.4.7. Hepatic Safety Monitoring

If a study patient with ALT and AST within the normal range at baseline experiences elevated transaminases greater than 2x ULN, then a repeat measurement should be performed within 48 - 72 hours. If elevations greater than 2x ULN persist, then subjects should be evaluated for other causes of transaminase elevation and with additional tests of hepatic status. Close observation for suspected DILI will be conducted. If no other cause is found, then investigational product should be discontinued (see guidelines in Section 8.1).

If a study patient with ALT and AST above the normal range at baseline develops further elevations of ALT or AST >2x the baseline value or a bilirubin >2x ULN during the study, then repeat testing should be performed within 48 - 72 hours. If there are persistent elevations (ALT or AST >2x baseline or bilirubin >2x ULN), then close observation for suspected DILI will be conducted. If no other cause is found, then discontinuation of investigational product should be considered (see guidelines in Section 8.1).

The decision to discontinue or temporarily interrupt investigational product should be considered based on factors that include how much higher than baseline ALT and AST were relative to the upper limit of normal (ULN) and how much the on-study ALT and AST levels have increased relative to baseline, in addition to whether there is concomitant elevation of bilirubin or INR (see guidelines in Section 8.1).

If the patient lives in a remote area, repeat laboratory testing and close monitoring can be performed locally and the results should be promptly communicated to the investigator.

Close Observation for Suspected DILI

- Repeat liver enzyme and serum bilirubin tests two or three times weekly. Frequency of repeat testing can decrease to once a week or less if abnormalities stabilize or the trial drug has been discontinued and the subject is asymptomatic.
- Obtain a more detailed history of symptoms and prior or concurrent diseases.

- Obtain a history of concomitant drug use (including nonprescription medications and herbal and dietary supplement preparations), alcohol use, recreational drug use, and special diets.
- Rule out acute viral hepatitis types A, B, C, D, and E; autoimmune or alcoholic hepatitis; NASH; hypoxic/ischemic hepatopathy; and biliary tract disease.
- Obtain a history of exposure to environmental chemical agents.

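### The baseline ALT/AST groups in Table JAIV.4, Section 8.1.2 and Section 9.4.7 do not agree for a patient with one enzyme normal and the other elevated, leaving conflicting resume and stop limits and no stated retest trigger

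*Protocol*

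**What the plan says.** **Hold and resume (Protocol Section 8.1.1, Table JAIV.4).** One row sets a hold above 3 x ULN "for patients with normal ALT or AST at baseline". The next sets it above 3 times the baseline "value for patients with ALT or AST >ULN at baseline". The table is mandatory: "Investigational product must be held in the following situations and may only be resumed as noted in the table". Under the first row, dosing may resume when both enzymes are at or below "3X ULN and investigational product is not considered the cause of enzyme elevation". Under the second, both must be at or below 3 x baseline, with the same condition on cause.

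**Permanent stop (Section 8.1.2).** List (a) is for patients with "baseline normal ALT and/or AST" and list (b) for those with "baseline elevated ALT and/or AST". Discontinuation is to be considered after consultation with the medical monitor when any one condition is met.

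**Retest and close observation (Section 9.4.7).** One branch opens "If a study patient with ALT and AST within the normal range at baseline experiences elevated transaminases greater than 2x ULN" and the other "If a study patient with ALT and AST above the normal range at baseline develops further elevations of ALT or AST". Each calls for a repeat test within 48-72 hours and, if the rise persists, leads to close observation for drug-induced liver injury. A later paragraph, not split by baseline, lists factors for interrupting or stopping and refers back to Section 8.1.

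**Entry (Section 6.2, criterion [29]).** ALT and AST are each excluded only above 3 x ULN, so a patient with one normal and one elevated enzyme can enrol.

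**The concern.** A rule that depends on baseline class should put each patient in exactly one class. Here the connecting word changes between sections: *or* in Table JAIV.4, *and/or* in Section 8.1.2, *and* in Section 9.4.7. The first two make the classes overlap for a mixed patient; the third leaves that patient out.

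These rules govern interruption, restart and permanent stopping in a liver-disease population in which, by the protocol's own account (Section 3.1), the drug has not been studied. Two sites could read the same laboratory result against different limits, each with support in the text, and a mixed patient could miss the retest that Section 9.4.7 specifies for the other patients.

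**Working it through.** The plan gives no figure to reproduce. The check applies the stated conditions to the four possible baseline classes and then to one illustrative patient.

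**Step 1: membership, read literally**

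| Baseline | Table JAIV.4 row 1 (x ULN) / list (a) | Table JAIV.4 row 2 (x baseline) / list (b) | 9.4.7 first branch | 9.4.7 second branch |
|---|---|---|---|---|
| Both normal | yes | no | yes | no |
| ALT only elevated | yes | yes | no | no |
| AST only elevated | yes | yes | no | no |
| Both elevated | no | yes | no | yes |

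Rows 1 and 2 here mean the two ALT/AST rows. The rules sort cleanly when the enzymes agree and fail only for the two mixed classes.

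**Step 2: hold and resume limits.** Assumed baseline: AST 2.0 and ALT 0.5 x ULN. Row 1 limit = 3 x ULN for either enzyme. Row 2 limit = 3 x baseline, so AST 3 x 2.0 = 6.0 x ULN and ALT 3 x 0.5 = 1.5 x ULN. On study, AST is 3.2 x ULN and ALT is unchanged.

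- Row 1: 3.2 > 3, so hold. Its resume limit is not met.
- Row 2: 3.2 < 6.0, so not triggered. Its resume limits are already met (3.2 <= 6.0 and 0.5 <= 1.5), subject to the drug not being judged the cause.

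For the elevated enzyme, the rows disagree between 3 x ULN and 3 x baseline. The upper end is 3.3, 4.5, 6, 7.5 and 9 x ULN for baselines of 1.1, 1.5, 2, 2.5 and 3 x ULN. For the normal enzyme the order reverses: at a baseline of 0.5 x ULN, row 2 triggers above 1.5 x ULN and row 1 only above 3 x ULN.

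**Step 3: two ways a site might resolve the overlap**

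| Reading | AST limit (baseline 2.0) | ALT limit (baseline 0.5) |
|---|---|---|
| Either row triggers; the lower limit binds | min(3, 6.0) = 3 x ULN | min(3, 1.5) = 1.5 x ULN |
| Each enzyme by its own baseline class | 6.0 x ULN | 3 x ULN |

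The two readings pick the opposite row for each enzyme. The second is not stated anywhere.

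**Step 4: stop lists**

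- *Analytes.* All five rows of list (a) name ALT or AST. Of the five transaminase rows in list (b), four name ALT only.
- *Confirmation.* Three rows of list (a) act on a single test. Apart from the row for values during an interruption, list (b) requires two tests.
- *Thresholds.* With ALT elevated at 2 x ULN and AST normal, a single ALT of 8.5 x ULN meets list (a) (> 8 x ULN) but not the relative limit in list (b) (5 x 2 = 10 x ULN, confirmed). List (b)'s alternative limit of 400 U/L might apply if confirmed; the documents give no ULN in U/L to check this.
- *Symptoms.* For the Step 2 patient, one AST of 3.2 x ULN with new fatigue meets list (a). The matching row of list (b) needs a confirmed ALT above 3 x baseline with severe fatigue or another listed feature, and has no AST version.
- *Shared row.* Both lists contain the confirmed rise above 2 x ULN with no other known cause.

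**Step 5: retest.** The first branch of Section 9.4.7 starts at 2 x ULN and the second at 2 x baseline (AST 2 x 2.0 = 4.0 x ULN here). The mixed patient belongs to neither, so no ALT or AST value triggers the 48-72 hour repeat or close observation.

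**The case against.** **Hold and continue.** A reader might infer that one result means both hold and continue. The text does not support that. The rows of Table JAIV.4 are separate triggers, any one of which requires a hold, and not meeting row 2 is no instruction to keep dosing. The literal text yields a strict hold rule. One can add that each resume entry belongs to its own row, so a row 1 hold ends under row 1. That is a reasonable reading, but row 2's resume entry is written for patients with a raised baseline, which this patient has, and nothing ranks the two. Section 8.1.2 also sends restarts back to these resume limits.

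**Stop lists.** A patient in both lists can be assessed against both, the shared row gives the same answer for confirmed unexplained rises, and the medical monitor is consulted. All this stands and narrows the practical difference for permanent stops. It does not cover holds: Section 8.1.1 recommends consulting the sponsor only for interruptions outside the table.

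**Enzyme-by-enzyme reading.** This would remove the overlap in Table JAIV.4. It is unstated, cannot be applied to Section 9.4.7, which requires both enzymes, and fits poorly with the mostly ALT-only list (b).

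**Retesting.** The mixed patient is not without any recheck. Section 8.1.1 leaves retest timing to the investigator unless specified, the two-test stop rows presuppose a repeat, and the general paragraph of 9.4.7 applies to everyone. What is missing is the stated trigger and its time window.

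**The data monitoring committee.** A reader might infer that the Cohort A evidence depends on how sites read these rows. That goes too far. Under Section 9.4.8.2 the committee may be convened after two or more permanent safety discontinuations, with the chair deciding on a full meeting. It also sees laboratory results and adverse events directly (SAP Section 6.16.1).

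**Conclusion.** The point holds as a conflict between stated rules for one identifiable type of eligible patient. That patient has two resume limits, two stop lists that differ in threshold, analyte and confirmation, and no stated ALT/AST trigger for the 48-72 hour repeat or close observation. For an elevated enzyme, the gap between the two hold limits grows with baseline and reaches 3 to 9 x ULN at the entry maximum of 3 x ULN.

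The membership result follows from the wording alone. The numerical examples use assumed enzyme values. The documents do not say how many patients will have mixed baselines, or how many would reach the ranges where the limits differ, so no count of affected patients is claimed. Because the rules concern patient safety and the remedy is wording, the conflict warrants correction rather than reliance on each site's reading.

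**What to change.** Reconcile Table JAIV.4 (hold and resume columns), lists (a) and (b) of Section 8.1.2, and both branches of Section 9.4.7 to one baseline classification, worded identically each time. It should place every patient, or every analyte if preferred, in exactly one group, and the rows should name the analytes that the classification needs. The sponsor's hepatic safety group should choose the classification and the thresholds; none is proposed here.

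The cost is protocol amendment wording and a memo to sites. No additional scheduled visits or patients are needed.

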8.1.2. Permanent Discontinuation from Study Treatment

Possible reasons leading to permanent discontinuation of investigational product:

- **Subject Decision**
 - the patient requests to discontinue investigational product.
- **Investigator Decision**
 - the investigator decides that the patient should be discontinued from investigational product
- **Discontinuation due to a hepatic event or liver test abnormality:** Patients who are discontinued from investigational product because of a hepatic event or liver test abnormality should have additional hepatic safety data collected via eCRF. Details on continued hepatic monitoring are provided in Section 9.4.7.

If multiple values are obtained during screening, the highest value prior to receipt of investigational product will be used as baseline. Discontinuation of the investigational product for abnormal liver tests **should be** considered by the investigator when a patient meets one of the following conditions after consultation with the Lilly designated medical monitor:

- a. For patients with **baseline normal ALT and/or AST**, the following will result in discontinuation:

single laboratory test	ALT or AST >8 x ULN
single laboratory test	ALT or AST >3 x ULN and TBL >2 x ULN or International Normalized Ratio (INR) >1.5
single laboratory test	ALT or AST >3 x ULN with the appearance of fatigue, nausea, vomiting, right upper-quadrant pain or tenderness, fever, rash, and/or eosinophilia (>5%)
confirmed laboratory test (2 tests)	ALT or AST >2 x ULN and no other known cause.
during temporary interruption of IP	ALT or AST >5 x ULN for more than 2 weeks after temporary interruption of investigational product

- b. For patients with **baseline elevated ALT and/or AST**, the following will result in discontinuation:

confirmed laboratory test (2 tests)	ALT >5 x baseline, or >400 U/L (whichever occurs first)
confirmed laboratory test (2 tests)	ALT >3 x baseline and TBL >2 x ULN or INR >1.5
confirmed laboratory test (2 tests)	ALT >3 x baseline with appearance of severe fatigue, nausea, vomiting, right upper-quadrant abdominal pain, fever, rash, and/or eosinophilia (>5%)
confirmed laboratory test (2 tests)	ALT or AST >2 x ULN and no other known cause
confirmed laboratory test (2 tests)	TBL >1.5 x baseline upon retesting and no other known cause
during temporary interruption of IP	ALT >4 x baseline or >300 U/L (whichever occurs first) for more than 2 weeks after temporary interruption of investigational product

- c. For **all patients**, the following will result in discontinuation:

confirmed laboratory test (2 tests)	ALP >3 x baseline and >6 x ULN
confirmed laboratory test (2 tests)	ALP >2.5 x baseline and TBL >2 x ULN or INR >1.5
confirmed laboratory test (2 tests)	ALP >2.5 x baseline with appearance of severe fatigue, vomiting, right upper-quadrant pain, fever, rash, and/or eosinophilia (>5%)

- **Discontinuation due to other laboratory abnormalities:**

- White blood cell count <1000 cells/ μ L ($1.00 \times 10^3/\mu$ L or 1.00 GI/L)
- Absolute neutrophil count <500 cells/ μ L ($0.50 \times 10^3/\mu$ L or 0.50 GI/L)
- Lymphocyte count <200 cells/ μ L ($0.20 \times 10^3/\mu$ L or 0.20 GI/L)
- Hemoglobin <6.5 g/dL (<65.0 g/L)
- Creatine phosphokinase >5x ULN
- eGFR ≤ 40 mL/min/1.73m².

Temporary interruption rules (Section 8.1.1) must be followed where applicable. For laboratory values that meet permanent discontinuation thresholds, investigational product should be discontinued. However, if in the opinion of the investigator, the laboratory abnormality is due to intercurrent illness or another identified factor, laboratory tests may be repeated. The investigator may be able to restart investigational product after consultation with the Lilly designated medical monitor, only when the laboratory value meets resumption thresholds (Table JAIV.4) following the resolution of the intercurrent illness or other identified factor.

- **Discontinuation due to other circumstances:**

- pregnancy
- malignancy (except for successfully treated basal cell or squamous epithelial skin cancers)
- occurrence of a VTE (DVT/PE)
- serious infection that, in the opinion of the investigator, merits the investigational product being discontinued
- if the patient, for any reason, requires treatment with another therapeutic agent that may be effective for treatment of PBC that is listed in the exclusion criteria (Section 6.2) or is noncompliant to the concomitant therapy requirements (Section 7.6) during the study. Discontinuation from the investigational product must occur prior to introduction of the new agent.

Throughout the study, investigators should continue to assess benefit/risk for patients to remain in the trial and should consider discontinuing patients if sufficient clinical benefit is not observed with protocol allowed concomitant treatments.

Patients discontinuing from the investigational product prematurely for any reason should complete AE and other follow-up procedures per Section 2 (Schedule of Activities), Section 9.2 (Adverse Events), and Section 9.4 (Safety) of this protocol.

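### Hepatic stopping row b4 in Section 8.1.2 uses >2 × ULN for patients with raised baseline ALT or AST, so an eligible patient unchanged above 2 × ULN already meets its number; the lead-in and list headings also differ in force.

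*Protocol*

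**What the plan says.** Rows are numbered here in order within each list of Protocol Section 8.1.2: a1 to a5 (normal baseline ALT and/or AST), b1 to b6 (raised baseline), c1 to c3 (all patients, ALP).

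- **Lead-in to the lists.** Stopping for abnormal liver tests is something to be "considered by the investigator when a patient meets one of the following conditions after consultation with the Lilly designated medical monitor".
- **Headings of lists a, b and c.** Each says "the following will result in discontinuation". The rows they govern include c1, "ALP >3 x baseline and >6 x ULN".
- **Paragraph after the other-laboratory bullets.** "For laboratory values that meet permanent discontinuation thresholds, investigational product should be discontinued". Tests may be repeated if the investigator attributes the abnormality to another illness or identified factor. Restart is then possible "only when the laboratory value meets resumption thresholds (Table JAIV.4) following the resolution of the intercurrent illness or other identified factor".
- **Row b4.** On two tests, "ALT or AST >2 x ULN and no other known cause". The same words form row a4.
- **Baseline for the liver rules.** The highest pre-dose value when several were taken.
- **Section 8.1.1.** "Investigational product must be held in the following situations and may only be resumed as noted in the table". Table JAIV.4 sets the hold at >3 × ULN for a normal baseline and >3 × baseline for a raised one.
- **Section 9.4.7.** With ALT and AST above normal at baseline, a retest is triggered at >2 × baseline for either enzyme, or by bilirubin >2 × ULN. If the rise persists unexplained, stopping is to be considered. A further paragraph tells the investigator to weigh how far baseline was above ULN and how far values have risen since.
- **Section 6.2.** Criterion 29 excludes ALT or AST above 3 × ULN and total bilirubin above ULN. Criterion 44 excludes a second screening ALT, AST or bilirubin that is above ULN and more than 20% higher than the first.

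**The concern.** A liver stopping rule should tell every site the same thing and should react to a change after dosing. Section 8.1.2 falls short on both counts. The same rows are discretionary in the lead-in and mandatory in the headings. Row b4 carries the limit for a normal baseline into the list for a raised baseline, so it can describe a patient in whom nothing has happened.

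This matters because Section 3.3 lists hepatotoxicity as an important potential risk and Section 3.1 says baricitinib has not been studied in PBC. Read literally, b4 could permanently stop a stable patient. If it is routinely explained away by the underlying disease, it gives little protection against real drug injury. A permanent stop also removes that patient's later ALP values from the primary MMRM (Protocol Section 10.3.1.2; SAP Section 6.3).

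**Working it through.** The plan states no figure on this point, so the check compares thresholds.

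**Inputs.** Let r = baseline ALT or AST divided by ULN.
- Raised baseline: r > 1. Eligible: r ≤ 3 (criterion 29). A stable value also passes criterion 44.
- b4 limit: 2 × ULN.
- Section 9.4.7 trigger: 2 × baseline = 2r × ULN.
- Table JAIV.4 hold: 3 × baseline = 3r × ULN.

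**Formulas.** b4 limit as a multiple of baseline = 2/r. Change needed to reach it = (2/r − 1) × 100%. An unchanged value meets b4 numerically whenever r > 2.

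| r | 2/r | Change needed to reach 2 × ULN | 9.4.7 trigger (× ULN) | Hold (× ULN) |
|---|---|---|---|---|
| 1.1 | 1.82 | +81.8% | 2.2 | 3.3 |
| 1.5 | 1.33 | +33.3% | 3.0 | 4.5 |
| 2.0 | 1.00 | 0% | 4.0 | 6.0 |
| 2.5 | 0.80 | −20.0% | 5.0 | 7.5 |
| 3.0 | 0.67 | −33.3% | 6.0 | 9.0 |

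For 2 < r ≤ 3 the patient is eligible and over the b4 number before the first dose. At r = 2.5, two unchanged results satisfy the two-test requirement. If scheduled visits count as the two tests, this can happen at Weeks 1 and 4. Section 9.4.7 describes a repeat within 48 to 72 hours, and an unchanged value meets b4 on that basis too. Section 9.4.7 itself would not ask for a retest on ALT or AST until either exceeded 5 × ULN, although bilirubin could trigger one separately.

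**Relation to the hold.** For every r > 1, b4's 2 × ULN is below the hold at 3r × ULN. That ordering alone is not the error: a4 (2 × ULN) is also below its hold (3 × ULN), and a confirmed, unexplained rise may justify a lower limit. What is particular to b4 is that the limit is at or below the patient's own baseline when r ≥ 2.

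**Force of the rows.** There are 5 + 6 + 3 = 14 hepatic rows. The lead-in says consider, the headings say will, and the later paragraph says should be discontinued. That paragraph refers to laboratory values meeting permanent discontinuation thresholds without limiting itself to one list. On that reading all 14 rows have an instruction to stop, and the lead-in is the text out of line.

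**Two checks on the remedy.**
- A plain limit of >2 × baseline for either enzyme fails when only one is raised. With baseline ALT 1.5 and AST 0.4 × ULN, AST would meet it just above 2 × 0.4 = 0.8 × ULN, a normal value.
- Row b5 is confirmed bilirubin >1.5 × baseline without another known cause. Since entry requires bilirubin no higher than ULN, any baseline below 1/1.5 = 0.67 × ULN gives a limit inside the normal range. At 0.5 × ULN the limit is 0.75 × ULN. Making all rows mandatory without amending b5 would force stops on normal bilirubin.

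**The case against.** The strongest reply is that the protocol already contains what is needed. Row b4 also requires that no other cause be known, and a pre-treatment elevation in a patient with PBC has an obvious candidate. Section 9.4.7 tells the investigator to weigh change from baseline, and the medical monitor is consulted. This limits how often b4 would stop an unchanged patient. It does not repair the row: the protocol never says whether PBC counts as the other cause, and Section 9.4.7 refers back to Section 8.1 for its guidelines.

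Three stronger readings are tempting but unsupported.

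- **That some rows, notably those on ALP and bilirubin, have no binding instruction.** Only the position of the later stop sentence, after the other-laboratory bullets, suggests this. Its wording is general.
- **That an ALP or bilirubin stop could be reversed freely.** The Section 8.1.1 clause under which product "may be restarted at the discretion of the investigator" concerns temporary interruptions. Restart after a permanent threshold depends on Table JAIV.4, which has no ALP or bilirubin row, so the default is no restart.
- **That the primary result is affected.** No rate of hepatic stops is given, so nothing can be computed.

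**Conclusion.** The concern holds in two parts of unequal weight.

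Row b4 is wrong as written. For every eligible ALT or AST above 2 and up to 3 × ULN it is met numerically without change, and at the cap it remains met until the value has fallen by a third. It is inconsistent with the twice-baseline trigger and the change-from-baseline factors in Section 9.4.7.

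The mixed wording of consider, will and should is a drafting conflict. The general stop sentence resolves it on its natural reading, but the lead-in still needs aligning.

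This rests on taking criterion 29's cap as the upper end of baseline and on b4's other-cause clause being left to judgement. The share of patients above 2 × ULN is unknown. The point concerns patient safety and consistency between sites, and a wording amendment should correct it.

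**What to change.** 1. **Row b4.** Replace with: *confirmed >2 × baseline for an enzyme (ALT or AST) above ULN at baseline, or >2 × ULN for an enzyme normal at baseline, and no other known cause*, with baseline as the highest pre-dose value. Both list headings say and/or, so a patient with one enzyme raised falls under both lists; restrict a4 to the enzyme that was normal at baseline.
2. **Lead-in.** State that product is permanently stopped when a row is met and that the medical monitor is informed. State that the later stop sentence and its exception for another illness or identified factor apply to lists a to c. Add to b5 that bilirubin must also exceed ULN.
3. **Section 9.4.7.** Make the raised-baseline paragraph refer to Section 8.1.2 for the stopping action, so that one value does not carry two forces.

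The cost is wording in two sections plus site training. No visit or test is added, since repeat testing is already in Section 9.4.7. Investigators lose a little discretion. For raised-baseline enzymes the b4 stop moves from 2 × ULN to between 2 and 6 × ULN (2r for r from 1 to 3). Rows b1 to b3, b5 as amended, and the >3 × baseline hold stay in place. The sponsor's hepatologist should confirm the b4 limit near the cap and the b5 amendment.
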